3. INVESTIGATIONAL PLAN

3.1. Overall Study Design and Plan

This is a Phase 1, open-label, randomized, 2-way crossover, 3-period study. A single oral dose of LOXO-305 will be administered under fasted conditions (Treatment A) and fed conditions (Treatment B). Multiple oral doses of omeprazole will be administered once daily from Day 15 through Day 18, with a single oral dose of LOXO-305 co-administered with omeprazole under fasted conditions on Day 18 (Treatment C). PK sampling will be obtained for 168 hours after administration of each dose of LOXO-305 (ie, on Days 1, 8, and 18). The 2 treatment sequences will be ABC and BAC. Subjects will be randomly assigned to 1 of the 2 treatment sequences, according to a randomization scheme issued by Covance.

In Treatment A, a single oral dose of 200 mg LOXO-305 will be administered in the morning on Day 1 or Day 8 (according to the randomization scheme), following a fast of at least 10 hours prior to and 4 hours after dosing. In Treatment B, a single oral dose of 200 mg LOXO-305 will be administered in the morning on Day 1 or Day 8 (according to the randomization scheme), approximately 30 minutes after starting a standard breakfast. In Treatment C, a single oral dose of 40 mg omeprazole will be administered in the morning on Days 15, 16 and 17, following a fast of at least 8 hours prior to omeprazole dosing, followed by a standard breakfast administered approximately 1 hour after dosing. On Day 18, a single oral dose of 40 mg omeprazole will be co-administered with a single oral dose of 200 mg LOXO-305 in the morning, following a fast of at least 10 hours prior to and 4 hours after omeprazole and LOXO-305 co-administration. Standard breakfasts should be entirely consumed within 30 minutes. Serial PK blood samples for the analysis of plasma concentrations of LOXO-305 will be collected from predose through 168 hours postdose for each treatment.

There will be a washout period of 7 days between the doses of LOXO-305 administered in Treatments A and B, and a washout period of 7 days between the doses of LOXO-305 administered in Treatments A or B and the first dose of omeprazole in Treatment C.

To assess their eligibility to enter the study, potential subjects will be screened within 28 days (Days -29 to -2) and be admitted to the Clinical Research Unit (CRU) on Day -1 (Check-in). Replacement subjects may be enrolled only if deemed necessary by the Sponsor.

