| | | | | | | | | | | | | | S | tudy | v Daj | ys | | | | | | | | | | | Clinic Discharge/ EOT (Day 25) or ET ^v | Follow -up Phone Call (EOS) |
|--|----------------------------------|---|---|---|---|---|---|---|---|---|---|----|----|------|-------|----|----|----|----|----|----|----|----|----|----|----|---|---|
| Study Procedures ^a | Screening (Days -29 to -2) | | | 2 | 3 | 4 | 5 | 6 | 7 | 8 | 9 | 10 | 11 | 12 | 13 | 14 | 15 | 16 | 17 | 18 | 19 | 20 | 21 | 22 | 23 | 24 | | 7 (±2) days post EOT or ET ^w |
| Prior and Concomitant Medications ^s | X | Х | Х | X | Х | X | X | X | Х | Х | Х | X | Х | X | Х | X | X | X | X | X | X | Х | X | X | X | X | Х | Х |
| Serum Pregnancy Test ^t | Х | Х | | | | | | | | | | | | | | | | | | | | | | | | | Х | |
| FSH Test ^u TSH Test | X X | | | | | | | | | | | | | | | | | | | | | | | | | | | |

Abbreviations: AE = adverse event; BMI = body mass index; BP = blood pressure; CBC = complete blood count; CK = creatine kinase; CRU = Clinical Research Unit;

ECG = electrocardiogram; EOS = End of Study; EOT = End of Treatment; ET = Early Termination; FSH = follicle-stimulating hormone; HbA1c = hemoglobin A1c; HDYF? = How Do You Feel?; HIV = human immunodeficiency virus; ICF = Informed Consent Form; PK = pharmacokinetic; SAE = serious adverse event; TSH = thyroid-stimulating hormone; UA = urinalysis.a. For details on study procedures, see Section 7.

b. Interim medical history only.

c. Weight and BMI (based on Screening height) only.

d. A complete physical examination will be performed at Screening. An abbreviated physical examination will be performed at Check-in (Day -1) and at EOT (Day 25).

- e. 12-lead ECGs will be collected after the subject has rested in the supine position for at least 10 minutes, and will be obtained prior to and as close as possible to the scheduled blood draws at Screening and Day -1, Day 1 (predose and 2 hours after LOXO-305 dosing), Day 4 (ie, 72 hours after LOXO-305 dosing on Day 1), Day 8 (predose), Day 11 (ie, 72 hours after LOXO-305 dosing on Day 8), Day 15 (predose), Day 18 (predose), Day 21 (ie, 72 hours after LOXO-305 dosing on Day 18), and at EOT/Day 25 (168 hours after LOXO-305 dosing on Day 18) or ET.

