- f. Vital signs measurements (supine BP and pulse rate) will be obtained at Screening and Day -1, Day 1 (predose and 2, 4, 8, and 12 hours after LOXO-305 dosing), Day 2 (ie 24 hours after LOXO-305 dosing on Day 1), Day 4 (ie, 72 hours after LOXO-305 dosing on Day 1), Day 8 (predose and 2, 4, 8, and 12 hours after LOXO-305 dosing [on Day 8]), Day 9 (ie 24 hours after LOXO-305 dosing on Day 8), Day 11 (ie, 72 hours after LOXO-305 dosing on Day 8), Day 15 (predose), Day 18 (predose and 2 hours after LOXO-305 dosing on Day 18), Day 21 (ie, 72 hours after LOXO-305 dosing on Day 18), Day 25 (168 hours after LOXO-305 dosing on Day 18) or ET. Vital signs measurements should be carried out prior to and as close as possible to having blood drawn. Blood pressure and pulse rate will be measured using the same arm for each reading after the subject has been supine for at least 5 minutes.

g. Oral temperature and respiratory rate will also be obtained at at Screening, Day -1, and at EOT/Day 25 (168 hours after LOXO-305 dosing on Day 18) or ET.

h. An HDYF? inquiry will be performed at Screening (after the ICF is signed), at Check-in (Day -1), at each postdose vital signs assessment, and at an appropriate time for all other days.

i. Adverse events and SAEs will be collected beginning at informed consent. Adverse events will be recorded throughout the study (ie, from signing of the ICF until EOS, or until ET if the subject discontinues from the study and does not complete a follow-up phone call), either as subject medical history (if the event is reported as beginning prior to signing of the ICF or if the event occurs prior to study drug administration on Day 1 and is assessed as not related to study procedures by the Investigator [or designee]) or as AEs (if the event occurs after signing of the

| Protocol | CONFIDENTIAL |
|------------------------|------------------------------------|
| Covance Study: 8422329 | Protocol Reference: LOXO-BTK-20014 |

ICF but prior to study drug administration on Day 1 and is assessed by the Investigator [or designee]) as related to study procedures, or if the event occurs after study drug administration on Day 1 through EOT or ET regardless of relationship to study drug). From EOT or ET through EOS, only AEs assessed as related to study drug are to be recorded. All SAEs that develop from the time of ICF signing until EOS (or ET if the subject discontinues from the study and does not complete a follow-up phone call) are to be reported.

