8.6. Safety and Tolerability Assessments

8.6.1. Adverse Events

All AEs will be coded using the Medical Dictionary for Regulatory Activities (MedDRA) Version 22.1. All AEs will be assigned severity grade using National Cancer Institute Common Terminology Criteria for Adverse Events (CTCAE) Version 5.0.

A treatment-emergent adverse event (TEAE) will be defined as an AE that starts during or after the first dose, or starts prior to the first dose and increases in severity after the first dose.

A treatment-related TEAE will be defined as a TEAE with a relationship of related to the study treatment (LOXO-305 or Omeprazole), as determined by the investigator.

The assignment of TEAEs to the associated treatments will be as follows:

- A TEAE occurring during or after Day 1 dosing and prior to Day 8 dosing will be assigned to '200 mg LOXO-305 (Fasted)' or '200 mg LOXO-305 (Fed)' depending on the subject's fasting status prior to Day 1 dosing.

- A TEAE occurring during or after Day 8 dosing and prior to Day 15 dosing will be assigned to '200 mg LOXO-305 (Fasted)' or '200 mg LOXO-305 (Fed)' depending on the subject's fasting status prior to Day 8 dosing.
- A TEAE occurring during or after Day 15 dosing and prior to Day 18 dosing will be assigned to '40 mg Omeprazole (Fasted)'.
- A TEAE occurring during or after Day 18 dosing will be assigned to '200 mg LOXO-305 + 40 mg Omeprazole (Fasted)'.

All AEs will be listed. In addition to the data recorded in the database, the listings will include derived onset time and duration. Onset time will be calculated from the time of the last dose for TEAEs only.

The frequency of subjects with TEAEs and the number of TEAEs will be summarized for the following categories:

- TEAEs (overall, serious, and leading to discontinuation) by treatment
- TEAEs by severity and treatment
- Treatment-related TEAEs (overall, serious, and leading to discontinuation) by treatment
- Treatment-related TEAEs by severity and treatment

The frequency of subjects will be summarized separately for TEAEs and treatment-related TEAEs by the following:

- System organ class, preferred term, and treatment
- Preferred term and treatment
- System organ class, preferred term, day of onset, and treatment

For the AE data the following rules will apply:

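### First-day adverse events are solicited less often for Treatment C (1 scheduled question) than for A or B (4 each), and only C's TEAE window has no end

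*Protocol*

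**What the plan says.** Protocol Appendix 4, footnote f, lists the vital-sign times. For the second dosing day it gives "Day 8 (predose and 2, 4, 8, and 12 hours after LOXO-305 dosing [on Day 8", with the same hours on Day 1. A 24-h reading follows on Days 2 and 9. For Treatment C it gives "Day 18 (predose and 2 hours after LOXO-305 dosing on Day 18), Day 21 (ie, 72 hours after LOXO-305 dosing on Day 18", with nothing on Day 19.

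Footnote h schedules the HDYF? question at Screening, at Check-in, and then "at each postdose vital signs assessment, and at an appropriate time for all other days". Protocol 7.2.1 repeats the rule. The number of questions on a dosing day therefore follows from the number of postdose vital-sign assessments.

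Protocol 3.1 fixes the order of treatments: "The 2 treatment sequences will be ABC and BAC". C is always last.

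SAP 8.6.1 assigns events to treatments by time. Events after the Day 1 dose count until Day 8 dosing, and events after the Day 8 dose until Day 15 dosing. Events on Days 15 to 18 before LOXO-305 go to omeprazole alone. Everything from Day 18 dosing onward goes to C, with no stated end. Under Protocol 3.1, from Day 25 (or early termination) until the follow-up call, only drug-related AEs and all SAEs are reported. The call is 7 ± 2 days later.

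The planned outputs in SAP 8.6.1 include "Treatment-related TEAEs (overall, serious, and leading to discontinuation) by treatment" and a table by "System organ class, preferred term, day of onset, and treatment".

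**The concern.** The secondary objective is safety and tolerability of LOXO-305 with food, without food and with the PPI. Its output is descriptive, with treatments side by side and no inferential analysis, so a reader works from raw counts.

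Those counts rest on unequal collection in two ways. Subjects on C are asked about their health less often on the day they take LOXO-305. They are also followed longer for related and serious events. If C shows fewer first-day TEAEs, or more related TEAEs, part of the difference could come from how often or how long events were sought. Neither document mentions this, so the tables would not warn the reader.

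**Working it through.** The plan states no figure on this point. The check is a count from the schedule.

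**Inputs**
- Postdose vital signs on the dosing day (footnote f): Day 1 at 2, 4, 8, 12 h; Day 8 at 2, 4, 8, 12 h; Day 18 at 2 h.
- Question rule (footnote h; Protocol 7.2.1): one per postdose vital-sign assessment. I count one on each non-dosing day.
- Window boundaries (SAP 8.6.1): Days 1, 8, 15 and 18.
- End of full AE reporting for completers: Day 25. Follow-up call: 5 to 9 days later (footnote w).

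**1. Scheduled dosing-day questions**
Day 1: 4. Day 8: 4. Day 18: 1.

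**2. Questions from dosing through the sixth day after**
- Day 1 dose: 4 + 6 (Days 2-7) = 10
- Day 8 dose: 4 + 6 (Days 9-14) = 10
- Day 18 dose: 1 + 6 (Days 19-24) = 7

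The whole difference, 10 − 7 = 3, lies on the dosing day. In addition, the next-day question is fixed at 24 h for A and B (Days 2 and 9) but has no set time on Day 19.

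**3. Event windows in subjects who complete**

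| | A or B, Day 1 dose | A or B, Day 8 dose | C, Day 18 dose |
|---|---|---|---|
| All AEs | 8 − 1 = 7 days | 15 − 8 = 7 days | 25 − 18 = 7 days |
| Related AEs and SAEs | 7 days | 7 days | 7 + 5 = 12 to 7 + 9 = 16 days |

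For related AEs and SAEs, C's window is 12/7 = 1.7 to 16/7 = 2.3 times as long; at the nominal call date it is 14/7 = 2.0 times. Omeprazole alone has 18 − 15 = 3 days.

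**4. Subjects who stop early**
A subject who terminates in period 1 or 2 has no next dose to close the window, and is still called 7 ± 2 days after termination. Related AEs and SAEs more than 168 h after A or B can therefore arise too. The 7-day figures for A and B in step 3 hold only for subjects who go on to the next period.

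**5. After the change proposed below**
Dosing-day questions become 4 / 4 / 4, and questions through the sixth day 10 / 10 / 10. The LOXO-305 onset window in the added summaries becomes 7 / 7 / 7 days.

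**The case against.** The strongest reply is that the scheduled question is only one source of AEs. Under Protocol 7.2.1, events also come from volunteered reports, examinations, ECGs, vital signs and laboratory tests. Subjects are confined and asked every day with a question that looks back to the last time of asking. An event on Day 18 reported on Day 19 keeps its own start time and is tabulated as Day 18 onset. Serial PK sampling also brings staff contact that day. All of this stands. It means that events on C are prompted less often, not that they go uncollected.

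On the window, the day-of-onset tables cover both all TEAEs and related TEAEs, so late events can be partly identified. The excess concerns only related AEs and SAEs that start more than 168 h after dosing. With the preliminary and uncertain half-life of about 18 h in Protocol 1.3.2, that is 168/18 = 9.3 half-lives, so few such events are to be expected. This also stands, but the overall, serious, discontinuation and severity tables are not split by onset.

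Stronger readings are tempting but unsupported:
- A reader might infer that C's TEAE counts are biased in a known direction. Fewer questions can lower them and a longer related/SAE window can raise some of them. The documents do not allow a net direction or size.
- A reader might infer that a 168-h cut-off would alter only C's column. Step 4 of the working shows that early terminators can alter A or B as well.
- A reader might add the ECG schedule: a 2-h ECG on Day 1 ("Day 1 (predose and 2 hours after LOXO-305 dosing), Day 4") but none on the later dosing days ("Day 8 (predose), Day 11 (ie, 72 hours after LOXO-305 dosing on Day 8), Day 15 (predose), Day 18 (predose), Day 21"). Questions are tied to vital signs, not to ECGs, so this does not bear on how often subjects are asked.

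**Conclusion.** The point holds as an avoidable, undisclosed difference in how events are sought. Scheduled dosing-day questions are 4 / 4 / 1, always to C's disadvantage because C is always in period 3. In subjects who complete, the window for related AEs and SAEs is 7 / 7 / 12-16 days, while the window for all AEs is equal at 7 days.

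The counts assume that footnote h is applied literally, with one question on each non-dosing day. The weight is limited: safety is secondary and descriptive, the primary PK comparisons are untouched, and much of the shortfall may be recovered by the other sources of AE reports. Equal collection would not remove the confounding of C with period. The change is worth making because it is cheap and these tables are the main output for the secondary objective.

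**What to change.** 1. **Protocol Appendix 4, footnote h.** Reconcile the Day 18/19 question times with those of Days 1/2 and 8/9, so that the HDYF? question is asked at 2, 4, 8, 12 and 24 h after each LOXO-305 dose. Footnote h alone can carry this, with no new vital-sign or ECG procedures. Vital-sign readings within 24 h would remain 5 / 5 / 1, so changes found only by measurement would still be sought unequally.
2. **SAP 8.6.1.** Add overall, serious, severity and treatment-related TEAE summaries limited to onset within 168 h of each LOXO-305 dose. Show later events separately, including those in subjects who terminate early after A or B. Keep omeprazole alone as its own column with its 3-day window stated. This equalises the window; it does not correct the number of questions.
3. **If the question schedule stays,** footnote the by-treatment and day-of-onset TEAE tables with the 4 / 4 / 1 counts.

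Cost: 3 more questions per confined subject (4, 8 and 12 h on Day 18), a fixed time for the existing Day 19 question, a minor protocol amendment with IRB review, and one extra set of tables. No extra stay is needed. Items 2 and 3 need no new data.

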Appendix 5: Protocol Amendment Summary of Changes

Protocol Version 2.0 (dated 29th January 2020) incorporated the following changes in Protocol Version 1.0 (dated 14th January 2020):

- The study duration has been extended to include an additional treatment (Treatment C) to assess the effect of a gastric pH change on the pharmacokinetics (PK) of LOXO-305 after multiple-doses of a proton pump inhibitor (PPI; omeprazole). The following changes were made:
 - The duration of confinement in the Clinical Research Unit has been extended from 16 days (Day -1 to Day 15) to 26 days (Day -1 to Day 25).
 - Clinic Discharge/End of Treatment (EOT) assessments that were conducted on Day 15 will now be conducted on Day 25.
 - Early Termination (ET) assessments that were conducted as per the assessments on Day 15 will now be conducted as per the assessments on Day 25.
 - All subjects will be administered a dose of 40 mg omeprazole once daily from Day 15 through Day 18, with a single oral dose of 200 mg LOXO-305 co-administered with omeprazole on Day 18 (Treatment C).
 - The treatment sequences AB and BA to be used in the randomization have been updated to ABC and BAC.
 - On Day 15 to Day 17, single oral doses of 40 mg omeprazole will be administered following a fast of at least 8 hours prior to dosing, followed by a standard breakfast administered approximately 1 hour after dosing. On Day 18, a single oral dose of 40 mg omeprazole will be coadministered with a single oral dose of 200 mg LOXO-305 in the morning, following a fast of at least 10 hours prior to and 4 hours after dosing omeprazole and LOXO-305 co-administration.
 - There will be a washout period of 7 days between dosing of LOXO-305 on Day 8 and the first dose of omeprazole on Day 15.

CCI

- o Additional safety monitoring assessments will be conducted as follows:
 - Concomitant medication, adverse event, and serious adverse event monitoring, and How do you feel? Inquiry will be conducted on Day 15 through Day 25.
 - Vital signs (blood pressure and pulse rate) and electrocardiogram assessments will be conducted at Day 15 (predose), Day 18 (predose and 2 hours after LOXO-305 dosing on Day 18), and Day 21 (ie, 72 hours after LOXO-305 dosing on Day 18).
 - Clinical laboratory evaluations will be conducted on Day 17 and Day 21.

• Rationale for the amended study design and selection of omeprazole dose has been included.

LOXO-305 is formulated with excipients that cause release of LOXO-305 from the formulation to be somewhat slower under acidic conditions than neutral conditions, and the clinical impact of this slower dissolution is unknown. The additional treatment will allow the Sponsor to assess the effect of reduced stomach acidity on the PK of LOXO-305 by raising the gastric pH with omeprazole, a PPI.

Additionally, the following clarifications and updates were made:

- Previously, the Schedule of Assessments incorrectly stated that oral body temperature and respiratory rate assessments would be conducted on Day 1, Day 4, Day 8, and Day 11; the Schedule of Assessments has been updated to reflect that oral body temperature and respiratory rate assessments will be conducted at Screening, Day -1, and EOT/Day 25 or ET only.
- Exclusion criterion #8 has been updated to remove the requirement for polymerase chain reaction confirmation to detect presence of an active virus before enrolment for subjects who are positive for hepatitis B surface antigen (HBsAg), hepatitis C virus (HCV), or human immunodeficiency virus (HIV) by antibody. Therefore, any subject who is positive for HBsAg, HCV, or HIV by antibody will be excluded.
- The PK parameter, area under the concentration-time curve from hour 0 to 24 hours (AUC₀₋₂₄), will be analysed as part of the mixed effects model.
- The inclusion of the PK parameter, apparent first order terminal elimination rate constant (Kel), is redundant as apparent terminal elimination rate constant (λ_Z) will be calculated.
- The statistical comparisons of interest are now:
 - Treatment A compared with Treatment B
 - Treatment A compared with Treatment C.
- In exclusion criterion #16 and concomitant medications and other restrictions, it has been clarified that while concomitant medication of PPIs is prohibited, this is with the exception of omeprazole administered for the purposes of this study and in accordance with the Protocol.

Minor updates:

- The synopsis and study title was updated accordingly to the changes in the protocol body, as applicable.
- The amendment/version number and date were updated throughout the protocol.
- Typographical errors and formatting errors were corrected, and minor clarifications were made, as necessary.

Abbreviations pertain to the statistical analysis plan (SAP) only (not the tables, figures, and listings [TFLs]).

ADaM	analysis data model
AE	adverse event
AUC ₀₋₂₄	area under the concentration-time curve from Hour 0 to 24 hours postdose
AUC _{0-t}	area under the concentration-time curve from Hour 0 to the last measurable concentration
AUC _{0-inf}	AUC extrapolated to infinity
%AUC _{extrap}	percentage extrapolation for area under the concentration-time curve extrapolated to infinity
BLQ	below the limit of quantification
CDISC	Clinical Data Interchange Standards Consortium
CI	confidence interval
CL/F	apparent systemic clearance
C _{max}	maximum observed plasma concentration
CRU	Clinical Research Unit
CSR	clinical study report
CTCAE	Common Terminology Criteria for Adverse Events
CV	coefficient of variation
ECG	electrocardiogram
EOS	End of Study
EOT	End of Treatment
ET	Early Termination
GLSM	geometric least squares mean
ICF	informed consent form
ICH	International Council for/Conference on Harmonisation of Technical Requirements for Registration of Pharmaceuticals for Human Use
λ _Z	apparent terminal elimination rate constant
ln	natural log
LSM	least squares mean
MedDRA	Medical Dictionary for Regulatory Activities
NC	not calculated
NR	no result
PK	pharmacokinetic(s)
PPI	proton pump inhibitor
SAE	serious adverse event
SAP	statistical analysis plan

SD	standard deviation
TEAE	treatment-emergent adverse event
TFL	table, figure, and listing
$t_{1/2}$	apparent terminal elimination half-life
t_{max}	time to maximum observed concentration
WHODrug	World Health Organization Drug Dictionary

1. INTRODUCTION

This SAP has been developed after review of the clinical study protocol (Final Version 2.0 dated 29 January 2020) and electronic case report form.

This SAP describes the planned analysis of the pharmacokinetic (PK), and safety and tolerability data from this study. A detailed description of the planned TFLs to be presented in the clinical study report (CSR) is provided in the accompanying TFL shells document.

In general, the analyses are based on information from the protocol, unless they have been modified by agreement with Loxo Oncology, Inc. A limited amount of information about this study (eg, objectives, study design) is given to help the reader's interpretation. This SAP must be finalized prior to the lock of the clinical database for this study. When the SAP and TFL shells are approved, they will serve as the template for this study's CSR.

This SAP supersedes any statistical considerations identified in the protocol; where considerations are substantially different, they will be so identified. If additional analyses are required to supplement the planned analyses described in this SAP, they may be performed and will be identified accordingly in the CSR. Any substantial deviations from this SAP will be agreed with Loxo Oncology, Inc. and identified in the CSR.

This SAP is written with consideration of the recommendations outlined in the International Conference on Harmonisation (ICH) E9 guideline *Statistical Principles for Clinical Trials* and ICH E3 guideline *Structure and Content of Clinical Study Reports*.^{1,2}

The document history is presented in [Appendix 1](#).

